## 2.2 FOLLOW-UP TIME

- Enrolled COPD participants will be followed for a 3-month observation period (index date until End of Study visit) or until premature discontinuation from study, whichever occurs first.
- Participants in the calibration cohort will be followed for a 2-week observation period from index date.

## 2.3 OUTCOME DEFINITIONS

### 2.3.1 Outcomes for primary objectives

The primary outcomes are based on COPD exacerbations. Exacerbations are classified as

- 1) mild if they are treated with short-acting bronchodilators only,
- 2) moderate if they are treated additionally with antibiotics or oral corticosteroids, or
- 3) severe if the patient visits the emergency room or requires hospitalization because of an exacerbation.

The occurrence of exacerbations during the observation period is measured as follows.:

- For moderate/severe exacerbation requiring a physician's intervention, exacerbation details will be recorded via eCRF by the clinical site. Severity, onset and duration will be derived according to the definition above from the documented COPD medication associated with the patients' exacerbation visit. The definition details for COPD medication and ATC codes will be finalized during the planned Data review meeting prior to the final analysis.
- For mild exacerbations: self-reported; treated by the participant without intervention by a physician will be documented in the patient application labeling section (days with added treatment: short-acting bronchodilators only). The start date and end date of addition of short-acting bronchodilators can thus be retrieved from the patient application. The documented use of additional medication (Bedarfsmedikament) will be considered as a mild exacerbation with the following rules for start and end days:
  - A mild exacerbation must start with at least 2 consecutive days of additional medication reported, the first day of consecutive medication will determine the start of the exacerbation.
  - If there are gaps in the additional medication reporting, a maximum of 2 days is allowed to be considered only one exacerbation. A minimum of 70% of the days must have additional medication reported. The end date of the exacerbation is the last day where both these rules are fulfilled.
- Any exacerbations that happen within 5 days will be considered as overlapping, as well as exacerbations that have an intersection in their start and end dates. Overlapping exacerbations will be considered as only one and classified as the graver one. (4)
  - If all overlapping exacerbations have the same type, the start date is the start date of the first exacerbation, and the end date of the last one.

- If the overlapping exacerbations have different types, the start date will be the start date of the first moderate or severe exacerbation, and the end date is the end date of the last moderate or severe exacerbation.

The following exacerbation-related outcomes are required for the analysis of primary objectives:

1. Time points (start and end dates) of mild/moderate/severe exacerbations for descriptive analysis of sensor variables (see Section 2.1.4)
2. Occurrence of moderate/severe exacerbations as binary outcome measured at the onset date of an exacerbation for predictive analysis. An event is the occurrence of a moderate/severe exacerbation. Non-exacerbation events (for definition see Section 1.3.2) will be sampled randomly from time points (days) outside of exacerbation periods (defined by start and end dates of each exacerbation) and avoiding 2 weeks before the onset time (day) and two weeks after the end time (day) of an exacerbation.

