9.1.2.1 Primary Outcomes

The primary objective is to 1) describe the distribution of sensor collected data with COPD exacerbations, as well as 2) to predict COPD exacerbations by building a statistical model.

Severity of acute exacerbations of COPD (AECOPD) are defined using the GOLD definitions based on treatment consequences (event-based) ([Vogelmeier 2017](#)): AECOPDs are defined as “an acute worsening of respiratory symptoms that results in additional therapy”. Exacerbations are classified as 1) **mild** if they are treated with short-acting bronchodilators only; 2) **moderate** if they are treated with short-acting bronchodilators plus antibiotics and/or oral corticosteroids; or 3) **severe** if the patient visits the emergency room or requires hospitalization because of an exacerbation.

The occurrence of exacerbations during the observation period will be defined as follows:

- For moderate/severe exacerbation requiring a physician’s intervention, emergency room visit or hospitalization, the severity, date of the exacerbation, and the duration of the exacerbation will be recorded via an eCRF.
- For mild exacerbations: self-reported; treated by the participant without intervention by a physician will be documented in the patient application labeling section (days with added treatment).

The duration of exacerbations during the observation period will be defined as follows:

The duration of a severe/ moderate exacerbation will be derived from the duration of added medication from the group of systemic corticosteroids and/or antibiotics which define moderate exacerbations by GOLD. Days in-hospital for severe exacerbations will also be captured.

The duration of mild exacerbations will be derived from the event “additional relieve medication taken” noted in the labelling section of the patient facing applicaton (which defines mild exacerbations). Duration and start / stop will be derived from these patient entries.

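### SAP 2.3.1 can date the end of a mild exacerbation one, two or more days after the last reported medication, because the end date need not be a medicated day

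*SAP*

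**What the plan says.** Protocol 9.1.2.1 bases mild exacerbations on the participant's app entries for additional reliever medication and says: "Duration and start / stop will be derived from these patient entries".

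SAP 2.3.1 turns this into an algorithm.

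- **Purpose of the dates:** "The start date and end date of addition of short-acting bronchodilators can thus be retrieved from the patient application".
- **Start:** "A mild exacerbation must start with at least 2 consecutive days of additional medication reported". The first of those days is the start date.
- **Gap rule:** where reporting has gaps, "a maximum of 2 days is allowed to be considered only one exacerbation".
- **70% rule:** "A minimum of 70% of the days must have additional medication reported".
- **End:** "The end date of the exacerbation is the last day where both these rules are fulfilled".

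A separate bullet then acts on completed episodes: "Any exacerbations that happen within 5 days will be considered as overlapping". Its sub-rule for episodes of the same type takes the first start and the last end. Its sub-rule for mixed types takes the dates of the moderate or severe episodes.

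**The concern.** The two conditions in the end-date sentence describe the record up to a given day. Both can still be true on days after the participant stopped reporting medication. Read as written, the sentence picks the last such day and not the last medicated day. The episode then contains days at its end with no entry behind them, although both documents present the dates as coming from the entries.

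The end date is used in several places:

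- **Objective 1 (SAP 3.4.5.1)** is repeated for mild exacerbations alone. It summarises sensor data from the end of the exacerbation to 14 days after, in 7-, 3- and 1-day sliding windows, and again at 14, 21 and 28 days.
- **Duration** is part of the Objective 3c outcome definition (SAP 2.3.2) and is tabulated by severity (SAP 3.4.5.11).
- **Control days for Objective 2 (SAP 2.3.1)** must lie more than two weeks from an exacerbation's onset and end. The text does not say whether mild episodes count here.

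A late end date labels the first recovery days as exacerbation and delays every window that follows.

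**Working it through.** The SAP gives no worked example, so there is no figure of its own to reproduce. The inputs are the start, gap, 70% and end rules of SAP 2.3.1.

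**Set-up.** Take an unbroken run of n medicated days followed by medication-free days, and look at day n + k. The 70% rule holds while n/(n + k) ≥ 0.70, that is, while k ≤ 3n/7.

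**Reading A: trailing medication-free days count as a gap.** The gap rule requires k ≤ 2, so the overrun is the smaller of 2 and 3n/7 rounded down.

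| Medicated days n | Last day meeting both rules | Share on that day | Why the next day fails | Overrun |
|---|---|---|---|---|
| 2 | 2 | 2/2 = 100% | 2/3 = 66.7% | 0 |
| 3 | 4 | 3/4 = 75% | 3/5 = 60% | 1 (+33%) |
| 4 | 5 | 4/5 = 80% | 4/6 = 66.7% | 1 (+25%) |
| 5 | 7 | 5/7 = 71.4% | gap of 3 | 2 (+40%) |
| 10 | 12 | 10/12 = 83.3% | gap of 3 | 2 (+20%) |

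Interrupted runs were checked by applying the rules to all 4,096 fourteen-day patterns that begin with two medicated days. The overrun was 0 days in 2,552, 1 day in 1,162 and 2 days in 382, and never more than 2. These patterns are equally weighted, so the counts show the bound and not how often it would occur in patients.

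**Reading B: a gap exists only between two medicated days.** Trailing days then never break the gap rule, and only the 70% rule limits them. The overrun is 3n/7 rounded down:

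- n = 5: end day 7 (5/7 = 71.4%), overrun 2.
- n = 7: end day 10 (7/10 = 70%), overrun 3.
- n = 10: end day 14 (10/14 = 71.4%; day 15 gives 10/15 = 66.7%), overrun 4.

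**Effect on the Objective 1 windows.** A 2-day delay is twice the 1-day window, two thirds of the 3-day window and two sevenths (29%) of the 7-day window.

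**Link to the 5-day merge.** The SAP does not say how the 5 days are counted. For 5 days on, 3 off, 5 on, the second start is 4 days after the last medicated day of the first run (merged), but the onsets are 8 days apart (not merged). For 5 on, 6 off, 5 on, the second start is day 12. Counted end to start, that is 12 − 5 = 7 days from the last medicated day (not merged), but 12 − 7 = 5 days from the Reading A end date (merged). With end-to-start counting, the end-date wording can therefore also change the number of mild episodes.

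**After the fix.** If the end date must be a medicated day, the overrun is 0 for every pattern, and medication on days 1 to 5 ends on day 5.

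**The case against.** The best defence is that a gap in reporting naturally lies between two reports, and that the same bullet speaks of the end of added bronchodilator use, so the intended end is plainly the last medicated day. That is very likely what the authors mean, and a careful programmer may code it so. The sentence as written does not say it, however, and restricting the meaning of gap does not supply it: as Reading B shows, the restriction removes the 2-day limit on trailing days and lengthens the overrun. The last medicated day follows only if the word day is taken to mean a medicated day.

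It is also fair that the Protocol says dates are derived from entries, which permits a derivation rule, and that mild exacerbations are exploratory with acknowledged reporting error (Protocol 7 and 9.9). Both points limit the importance of the matter. Neither explains why days without an entry should belong to the episode.

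A reader might go further and infer that the 5-day merge contradicts the 2-day and 70% rules, because runs they separate can be rejoined. The documents do not support that. The SAP first builds episodes and then merges completed ones, writes out a same-type sub-rule that covers two mild episodes, and cites a reference for the step. The gap and 70% rules still decide whether isolated days extend an episode. One can construct a pattern such as 2 days on and 3 off that merges into a single episode lasting the whole study, but it needs perfect repetition and a chaining of successive merges that the SAP does not state. Merging two mild episodes is a choice on which statisticians may differ, and is not an error.

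**Conclusion.** The point holds for the end date. As written, the rule places the end 1 day after the last reported medication for unbroken runs of 3 or 4 days and 2 days after it for runs of 5 or more, provided trailing days count as a gap. If they do not, the overrun reaches 3 days for a 7-day run and 4 for a 10-day run. Two-day runs are unaffected.

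The reach is limited to mild episodes: their end dates and durations, the Objective 1 windows after a mild exacerbation, and the control-day exclusion if it includes mild episodes. The planned Objective 3 correlation uses counts (SAP 3.4.5.3), which trailing days alone do not alter; they could do so only through an end-to-start merge. A reader might infer that the primary prediction target is affected. It is not: moderate and severe events come from the eCRF, mixed merges take their dates from the moderate or severe episode, and the 18-event requirement counts only those events. This should be corrected, but it does not threaten the main model.

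**What to change.** Replace the end-date sentence in SAP 2.3.1 with: *The end date is the last day with additional medication reported on which both rules are fulfilled.*

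Keep the 5-day merge, including for two mild episodes, and add two clarifications: whether the 5 days run from end to start or from onset to onset, and that the 2-day and 70% rules are not re-applied to a merged episode. In the control-day definition, say whether mild exacerbations trigger the two-week exclusion.

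The cost is a few sentences and a recoded derivation, with no new data. SAP 3.1 plans a single analysis after the last patient is out, and SAP 2.3.1 already schedules a data review meeting before it, so the change can be made ahead of that meeting.

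### When a mild exacerbation merges with a moderate or severe one, its dates are dropped, so days of that episode are analysed unflagged as pre- or post-exacerbation days and might be drawn as controls

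*SAP*

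**What the plan says.** **Merging.** SAP 2.3.1 counts exacerbations as overlapping when their dates intersect or when they lie within 5 days of each other. "Overlapping exacerbations will be considered as only one and classified as the graver one".

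**Dates of the merged event.** If all components are of one type, the event runs from the first start to the last end. For mixed types the rule is: "If the overlapping exacerbations have different types, the start date will be the start date of the first moderate or severe exacerbation". Its close is fixed in the same way, by the final component above mild grade. The mild component's own start and end are not carried forward.

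**Mild episodes.** The same section builds these from app-logged additional medication. An episode opens with at least two consecutive days, may contain gaps of up to two days, and needs medication on at least 70% of its days. No maximum length is set.

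**Where the dates are used.**
- Objective 1 (SAP 3.4.5.1): the 14 days before onset and the 14 days after the end, in 7-, 3- and 1-day sliding windows, plus days 14, 21 and 28 afterwards.
- Objective 4 (SAP 3.4.5.4): a repeat of the mixed-model analysis in the 14 days before moderate/severe events.
- Objective 2 (SAP 2.3.1): the event is placed at onset. Protocol 9.7.2.1 plans to explore how model performance depends on the time before the event.
- Control days (SAP 2.3.1): drawn outside exacerbation periods, "avoiding 2 weeks before the onset time (day) and two weeks after the end time (day) of an exacerbation". SAP 1.3.2 and Protocol 9.5 say that controls come from exacerbation-free periods.

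**Predictors.** The Objective 2 row of Protocol 14.1.2 lists scheduled and non-scheduled spray use. SAP 3.4.3 derives a daily count of additional medication, which SAP 3.4.5.1 also describes under Objective 1.

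**The concern.** By the SAP's own merge rule the mild days belong to the same event. Once their dates are dropped, they belong to no exacerbation period. Three things follow.

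- The Objective 1 profiles before and after an event, and the Objective 4 models, mix days before (or after) the episode with days inside it, and the output does not show which are which.
- Objective 2 is meant to show how many days ahead an event can be predicted. If a mild phase came first, lead time counted to the moderate/severe onset includes days when the participant was already logging the episode. The model may be given that log as an input. The reader cannot then separate early warning from recognition of an episode in progress.
- Mild days far enough from the retained dates might enter the control pool, against the intention stated in SAP 1.3.2.

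**Working it through.** **The plan's own figures.** These are not in dispute. With 18 events and at least 13 detected, the exact one-sided error at 0.50 is 0.0481 and the power at 0.85 is 0.958; 17 events give power 0.901. A Poisson mean of 60 × 0.5 = 30 gives P(at least 18) = 0.993. Dropout: 60 / 0.9 = 66.7, so 67. All three reproduce.

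**Day count under the SAP rules.** Call the retained onset day 0 and let an unbroken mild run start on day −L and continue to day −1.

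- Days of the merged episode inside the 14-day pre-onset window: min(L, 14).
- Days beyond the 14-day buffer, open to control sampling if the rule refers to merged events: max(0, L − 14).

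| L | Mild days among the 14 pre-onset days | Control-eligible mild days |
|---|---|---|
| 2 | 2 | 0 |
| 7 | 7 | 0 |
| 14 | 14 | 0 |
| 15 | 14 | 1 |
| 20 | 14 | 6 (days −20 to −15) |
| 28 | 14 | 14 |

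A mild tail running T days past the retained end follows the same two formulas on the other side.

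The run need not reach onset. A mild episode from day −15 to day −5 (11 days) still merges if a 5-day difference counts as within 5 days. It then puts 10 days (−14 to −5) in the pre-window and leaves day −15 open as a control.

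**Lead time.** Suppose a run starts on day −5 and the model alarms on day −3. From the retained onset the lead is 3 days. From the episode start it is 3 − 5 = −2 days: the alarm came two days after the episode began.

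**Illustration of size.** The documents give no frequency of reliever use. I assumed a constant, independent daily probability p, applied the SAP's mild-episode rules, placed the retained onset at random between days 28 and 84, and simulated 3,000 events per setting. In each range the lower figure merges only the nearest mild episode and the higher lets a chain of mild episodes merge, because the SAP does not say which applies. The last column assumes the merged-event reading of the sampling rule.

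| p (assumed) | Mean mild days among the 14 pre-onset days | Chance of any control-eligible mild day |
|---|---|---|
| 0.1 | 0.12 to 0.13 | 0% |
| 0.3 | 1.25 to 1.44 | 0.2% to 2.0% |
| 0.5 | 4.68 to 5.63 | 12.2% to 29.9% |
| 0.7 | 10.90 to 11.63 | 67.3% to 84.3% |

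Real use would cluster around events, and mild tails are not simulated. The table shows how strongly the effect depends on reliever use; it is not a forecast.

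**With full episode dates.** Windows and sampling then run from the earliest start to the latest end. Days of the same episode in the pre-window fall from min(L, 14) to 0, and control-eligible days from max(0, L − 14) to 0.

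**The case against.** **The anchor is the declared target.** Protocol 7 and 9.7.2.1 and SAP 2.3.1 all name moderate/severe exacerbations as what is to be predicted, and worsening treated with relievers is a legitimate precursor for an early-warning tool. This stands. A reader might infer that the anchor itself is wrong; the documents do not support that. Nor are the two merge rules at odds in principle: each keeps the first start and last end of the gravest class present. What is missing is any trace of the mild days.

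**Control contamination is not established.** A reader might infer that some controls will be exacerbation days. That needs mild days more than 14 days from the retained dates. No mild day before onset qualifies when the run starts within 14 days of it. It also needs the sampling rule to mean merged events. SAP 2.3.1 separately calls for mild start and end dates, and SAP 1.3.2 asks for exacerbation-free periods, so the other reading is open. This stands as an ambiguity to close.

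**Direction is not shown.** A reader might infer that performance will look better than it is. Mild days among controls would make cases and controls more alike and tend to lower discrimination. Mild days before onset may make late alarms easier. The net effect is unknown.

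**The eCRF date gives no support.** The protocol says that "the severity, date of the exacerbation, and the duration of the exacerbation will be recorded via an eCRF", whereas the SAP says "Severity, onset and duration will be derived according to the definition above from the documented COPD medication". It is tempting to read the eCRF date as an earlier onset that the SAP ignores. The protocol does not define that date as symptom onset, and it too derives moderate/severe duration from added medication.

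**App logs are noisy.** Protocol 9.9 warns that mild episodes may be under- or over-reported. In frequent reliever users an episode-start anchor could move onset back by weeks. This stands, and it is why that anchor belongs in a sensitivity analysis.

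**Conclusion.** The point holds in a bounded form. It follows from the text alone that a mixed-type merge drops the mild dates and that no rule flags or excludes those days. They therefore enter the Objective 1 and Objective 4 windows, and Objective 2 lead time can be counted from a date after the merged episode began.

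Per affected event the size is min(L, 14) of 14 pre-onset days for an unbroken run. How many of the roughly 30 expected events are affected, and by how much, depends on reliever use that the documents do not report. Sampling of mild days as controls is possible but not certain, and would tend to dilute discrimination.

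The study is exploratory and its models are to be validated later, which limits the harm. With as few as 18 events, though, a handful of mis-anchored ones could shift the lead-time results, and choosing the anchor after seeing the models would be data-driven.

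**What to change.** Amend SAP 2.3.1 before any model is fitted:

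1. Keep the graver classification, and keep moderate/severe onset as the primary anchor.
2. For every merged event also store an episode start (earliest start over all components) and an episode end (latest end). State whether chains of mild episodes merge.
3. State that control days are drawn outside the full episode dates, with the existing 14-day buffers added to those dates.
4. Flag mild-component days wherever they fall in the Objective 1 pre- and post-windows and the Objective 4 pre-window.
5. Report Objective 1 windows and Objective 2 lead-time performance from both anchors, with episode start as a sensitivity analysis.

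The cost is SAP wording and one extra derived date pair per event, from data already collected. Reported lead times from the second anchor may be shorter, and frequent reliever users will contribute fewer eligible control days. Event counts and classification do not move, so the 18 events and N = 67 stay as they are.
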